7.11. Pharmacokinetic/Pharmacodynamic Methods

The plasma concentrations for LY3857210 will be reported graphically and summarized descriptively across the study visits.

Exploratory model-based analyses may be conducted to assess the relationship of LY3857210 plasma concentrations to efficacy and/or safety outcomes.

Additional analyses may be conducted, as needed.

Data from this study may be pooled with data from other studies.

7.12. Safety Analyses

The general analysis of safety has been described in the Study CPMP SAP Version 5. However, additional ISA-specific safety considerations are described in the sections below.

7.12.1. Extent of Exposure

Duration of exposure (defined as time since first dose of study treatment to last dose of study treatment in days) to study drug will be summarized by treatment group using descriptive statistics; the summary will also include the total exposure in patient years.

Duration of exposure (days):

Date of last dose during the double-blind treatment period – Date of first dose for the treatment period + 1.

Total exposure in patient years will be calculated as follows:

Summary of duration (days) of exposures for all patients in the treatment group / 365.25.

7.12.2. Adverse Events

The general analysis of AEs has been described in the CPMP SAP Version 5.

This ISA will report TEAEs separately for the entire 8-week double-blind period, the 2-week post-treatment period, and the entire 10-week study. For TEAEs in the double-blind period, the baseline will be prior to first dose date.

A PTEAE is defined as an event that first occurs or worsens in severity after double-blind treatment phase (after Visit 7) and on or before study discontinuation. This ISA will report PTEAEs for the post-treatment period, as they are important for assessing withdrawal or abuse liability potential. The MedDRA LLT will be used in the post-treatment-emergent computation. The maximum severity for each LLT during the double-blind treatment period (Visits 3 through 7) will be used as a reference.

The baseline of PTEAE is from the first dosing date to Visit 7. The post-treatment phase will be included as postbaseline for this analysis. While unusual, it is possible to have a missing severity for events. **CCI**

[REDACTED] PTEAEs will be determined by comparing with treatment period.

PTEAEs will be summarized by PT and by PT within SOC in participants who received LY3857210.

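### The PTEAE reference is the worst severity at any time on treatment, so a symptom that resolves and returns no worse after Visit 7, under the same LLT, is not counted as a PTEAE

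*SAP*

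**What the plan says.** SAP Section 7.12.2 defines the event: "A PTEAE is defined as an event that first occurs or worsens in severity after double-blind treatment phase (after Visit 7"), with study discontinuation as the latest limit. It then fixes how first occurrence and worsening are judged:

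- Matching level: "The MedDRA LLT will be used in the post-treatment-emergent computation".
- Reference severity: "The maximum severity for each LLT during the double-blind treatment period (Visits 3 through 7) will be used as a reference".
- Baseline window: "The baseline of PTEAE is from the first dosing date to Visit 7".

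The reason given for reporting PTEAEs is that "they are important for assessing withdrawal or abuse liability potential". The PTEAE summaries cover LY3857210 recipients only.

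The same section also plans other AE tables: "This ISA will report TEAEs separately for the entire 8-week double-blind period, the 2-week post-treatment period, and the entire 10-week study". It states a TEAE baseline for one of these periods: "For TEAEs in the double-blind period, the baseline will be prior to first dose date". It states none for the 2-week period. Section 7.12.3 separately lists abuse liability and withdrawal potential, to be analysed under a sponsor guidance that is not reproduced in the documents.

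**The concern.** A withdrawal question compares the participant's state after stopping with the state just before stopping. The rule compares it with the worst state at any point in the preceding 8 weeks, whether or not the symptom was still present at the end.

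Take a participant with moderate headache in Week 1 that resolves, no headache in Weeks 2 to 8, and moderate headache shortly after Visit 7. The headache is new relative to the end of treatment, but it neither first occurs after Visit 7 nor exceeds the on-treatment maximum. It is not a PTEAE. Early symptoms that settle on treatment and return on stopping are among the patterns a withdrawal summary should be able to show. This one drops them unless they return worse. At stake is an undercount in a safety summary that the SAP itself links to withdrawal.

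**Working it through.** The plan gives no figure to reproduce here, so the check is of the rule's logic, followed by an illustration of size under stated assumptions.

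**1. The rule as a formula.** For one participant and one LLT, let *M* be the maximum severity over Visits 3 to 7, *E* the severity ongoing at Visit 7 (0 if resolved or never present), and *P* the severity after Visit 7.

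- Current rule: PTEAE if *P* > *M*.
- End-of-treatment reference: counted if *P* > *E*.

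**2. Direction.** Visit 7 lies inside the window over which *M* is taken, so *M* ≥ *E*. Any event with *P* > *M* also has *P* > *E*. Every event counted by the current rule is counted by the other, and the reverse does not hold. The difference has one direction.

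**3. Resolved-then-returning symptoms.** Here *E* = 0. Assume three grades (mild, moderate, severe); the documents do not list the levels. Under the current rule:

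| Worst on treatment | Returns mild | Returns moderate | Returns severe |
|---|---|---|---|
| Mild | not counted | counted | counted |
| Moderate | not counted | not counted | counted |
| Severe | not counted | not counted | not counted |

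So 3 of 9 pairs are counted and 6 are not. With *E* = 0 as the reference, all 9 are counted. A symptom that was severe at any time on treatment can never become a PTEAE under the same LLT.

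**4. What the size depends on.** Among participants with a given withdrawal symptom, the share missed because the symptom had occurred earlier and resolved is

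missed share = *q* × *r* × *m*

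where *q* is the probability that the same LLT occurred on treatment, *r* the share of those in whom it had resolved by Visit 7, and *m* the probability that the earlier maximum was at least the returning severity. The documents give none of the three.

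For illustration, assume a 60/35/5% mild/moderate/severe mix in both periods, with the two severities independent:

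*m* = 0.60 × 1 + 0.35 × (0.35 + 0.05) + 0.05 × 0.05 = 0.60 + 0.14 + 0.0025 = 0.7425.

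If on-treatment and post-treatment occurrence are independent, *q* equals the on-treatment incidence; at 10%, *q* × *m* = 0.10 × 0.7425 = 0.074. If they are associated, *q* follows from the odds ratio and an assumed 15% post-treatment incidence. For 30% on-treatment incidence and odds ratio 6, solve a(1 − 0.30 − 0.15 + a) / [(0.30 − a)(0.15 − a)] = 6 for the joint probability a. This gives a ≈ 0.098, *q* = a/0.15 ≈ 0.652, and *q* × *m* ≈ 0.484.

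Values of *q* × *m*, that is, with *r* = 1:

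| Assumed on-treatment incidence | Odds ratio 1 | Odds ratio 3 | Odds ratio 6 |
|---|---|---|---|
| 5% | 3.7% | 8.1% | 11.8% |
| 10% | 7.4% | 15.5% | 22.0% |
| 30% | 22.3% | 38.3% | 48.4% |

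Each entry is a ceiling for its row and column. It must be multiplied by *r*, and it takes every recurrence to be coded to the same LLT.

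**The case against.** The definition, the reference and the baseline window in Section 7.12.2 agree with one another. This is a deliberate choice, and nothing in the documents says that an end-of-treatment reference is the only proper one. That stands, and it is a reason not to replace the definition.

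Three stronger readings are tempting, and the documents do not support them.

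- *Every symptom that returns after stopping is lost.* It is not. A return at higher severity than the on-treatment maximum is counted, and so is a return coded to a different LLT.
- *The trial cannot see such an event anywhere.* This is not shown. If the TEAE definition in the SAP abbreviation list, which compares with the pretreatment state, governs the 2-week table, the headache in the example could appear there. The analysis under Section 7.12.3 may also capture it. Neither route can be confirmed: Section 7.12.2 states no baseline for the 2-week table, and the sponsor guidance and CPMP SAP Version 5 are not available. Part of Section 7.12.2, after the remark on missing severity, is redacted, so a further rule there cannot be excluded.
- *The rule favours drug over placebo.* Masking does rise with on-treatment incidence, but the PTEAE summary is planned for LY3857210 recipients only, so it contains no between-arm comparison to bias.

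It is also fair to object that an end-of-treatment reference admits chance recurrences of common symptoms. With only the LY3857210 arm shown there would be no background rate to judge them against. That stands too, and the fix has to deal with it.

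**Conclusion.** The point holds in limited form. In the PTEAE summary, and there only, a symptom that resolved on treatment and returns after Visit 7 at the same or lower severity under the same LLT is not counted. The effect can only be an undercount relative to an end-of-treatment reference.

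The logical size is 6 of 9 severity pairs on an assumed three-grade scale. The expected frequency is unknown. A reader might take the top of the illustrative table, 48%, as the share of withdrawal events hidden. That is not supported: the incidences, odds ratios and severity mix are all assumptions, and the table includes symptoms that never resolved. A symptom still ongoing at Visit 7 and unchanged afterwards would not be counted under either reference.

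This is a low-cost improvement to a safety summary, not an error in the plan.

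**What to change.** In SAP Section 7.12.2, keep the PTEAE definition as it is and add one supplementary row. For that row, take as reference the severity of the LLT ongoing at the end of the treatment phase as the section already defines it (Visit 7), with none if the event had resolved. Resolved-then-recurrent events then count, and the two rows side by side show how many depend on the reference. Anchoring at Visit 7 leaves the start of the post-treatment period unchanged. Show the placebo rate beside the supplementary row so that chance recurrences can be judged.

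It would also help to state the baseline for the 2-week post-treatment TEAE table, so that a reader knows whether such events appear there.

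The cost is a few lines of SAP text, one derived flag and one extra placebo column. The flag needs AE onset and end dates. The OA05 protocol leaves AE recording to the Master Protocol, so their availability should be confirmed. No visit or procedure changes.

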4.1. Overall Design

The Master Protocol CPMP describes the overall study design and study design rationale. This section describes visits and overall procedures unique to ISA OA05 for LY3857210 in addition to the procedures outlined in CPMP and CPMP(1).

Double-blind treatment period (Visits 3 through 7)

Each visit is an outpatient visit.

At Visit 3

- participants are randomly assigned to LY3857210 or placebo
- the site completes the OA05 baseline procedures and sample collection (excluding PK) prior to study intervention
- the site collects participants' vitals predose
- participants receive their oral study intervention
- the site completes PK sample collection, and
- the site instructs participants to continue with study restrictions and NRS diary entries before their visit discharge.

At Visits 4 through 7

- the site reviews available safety data and sample collection
- participants continue oral study intervention (not applicable for V7) and bring all study intervention bottles to each visit
- the site completes all sample collection and safety monitoring noted in the SoAs, and
- the site instructs participants to continue with study restrictions, NRS diary entries, and wearing of CCI before their visit discharge.

Double-blind posttreatment follow-up period (Visit 801)

- Participants must complete 1 posttreatment follow-up visit for safety and efficacy assessment at Visit 801 according to the SoA
- the site schedules Visit 801 approximately 2 weeks after Visit 7 or ED Visit, and
- at Visit 801, participants return the devices (CCI)

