7.12.3. Deaths, Other Serious Adverse Events, and Other Notable Adverse Events

TEAEs by PT will be reported.

The general summary of AEs is described in the CPMP SAP Version 5. Other AEs include

- Abuse liability and withdrawal potential following the most recent Lilly Guidance for Assessment of Abuse Potential during Clinical Development.
- Seizures FMQ both narrow and broad terms will be analyzed.

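### The post-treatment-emergent adverse event table, meant to inform withdrawal and abuse liability, covers LY3857210 recipients only and has no placebo column

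*SAP*

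**What the plan says.** SAP 7.12.2 defines a PTEAE as an event that first occurs or worsens after Visit 7 and up to study discontinuation. The reference is the participant's maximum severity for the same MedDRA lowest level term (LLT) during Visits 3 through 7. The section gives the purpose: "This ISA will report PTEAEs for the post-treatment period, as they are important for assessing withdrawal or abuse liability potential". It then sets the population of the summary: "PTEAEs will be summarized by PT and by PT within SOC in participants who received LY3857210". The redacted text in this section follows the sentence on missing severity and does not touch either statement.

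Three other places bear on the point.

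- The same section plans a separate output with no arm restriction: "This ISA will report TEAEs separately for the entire 8-week double-blind period, the 2-week post-treatment period, and the entire 10-week study". It fixes a baseline for one part of that output: "For TEAEs in the double-blind period, the baseline will be prior to first dose date".
- SAP 7.12.3 lists a further analysis: "Abuse liability and withdrawal potential following the most recent Lilly Guidance for Assessment of Abuse Potential during Clinical Development". That guidance is not among the documents.
- Protocol 4.1 describes the follow-up period as double-blind and does not limit it to one arm: "Participants must complete 1 posttreatment follow-up visit for safety and efficacy assessment at Visit 801 according to the SoA".

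**The concern.** Assessing withdrawal means asking whether events after stopping exceed what would have happened anyway. In people with knee osteoarthritis seen two weeks after their last treatment visit, some new or worsened events are expected whichever capsule they were taking. The concurrent placebo group, stopped at the same point and followed under the same blind, is what measures that background. A table that leaves it out shows which events occurred after LY3857210 but gives no basis for attributing them to stopping it.

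The error could go either way. Background events may be read as a withdrawal signal, or a real excess may be dismissed as background because no comparison was tabulated.

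**Working it through.** The documents give no PTEAE rate or precision target, so there is no planned figure to reproduce. The check has two parts.

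**1. Could the table have been two-armed, and does another output replace it?**

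- *Data.* Participants are randomised to LY3857210 or placebo, and Visit 801 is required of participants without restriction by arm, for safety as well as efficacy (Protocol 4.1).
- *Rule.* The PTEAE derivation needs only dated, severity-graded events and the treatment-period maximum per LLT. Nothing in it depends on the arm.
- *Practice elsewhere in the SAP.* Exposure "to study drug will be summarized by treatment group using descriptive statistics" (7.12.1), and registry AEs are given by treatment group and preferred term (7.20).
- *Substitute.* The TEAE report for the 2-week post-treatment period may show both arms. However, the visible text attaches the pre-first-dose baseline only to TEAEs in the double-blind period and states none for the 2-week period. The treatment-period severity reference is given only to PTEAEs. On the visible text, that report is not shown to be the same comparison.

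So nothing visible provides a placebo PTEAE summary, and nothing visible prevents one.

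**2. How much is left out, and what would the one-arm table show with no withdrawal effect?**

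Inputs: up to about 125 randomised and about 80% completing double-blind treatment (Protocol 9.5, SAP 6.2). The allocation ratio is redacted, so 1:1, 2:1 and 3:1 (LY3857210 to placebo) are assumed. The background rate p for a single preferred term is assumed to be 2%, with a range of 1% to 5%.

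Expected completers: 0.80 × 125 = 100.

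- 1:1 gives 100 × 1/2 = 50 on LY3857210 and 50 on placebo.
- 2:1 gives 66.7 and 33.3.
- 3:1 gives 75 and 25.

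Probability that the term appears at least once among n LY3857210 completers: 1 − (1 − p)^n. At p = 2% and n = 50, this is 1 − 0.98^50 = 0.636. Expected number of placebo completers with the term: n(placebo) × p. At p = 2% and 1:1, this is 50 × 0.02 = 1.00.

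| p | Appears in LY3857210 table (1:1, 2:1, 3:1) | Expected placebo count (1:1, 2:1, 3:1) |
|---|---|---|
| 1% | 0.395, 0.488, 0.529 | 0.50, 0.33, 0.25 |
| 2% | 0.636, 0.740, 0.780 | 1.00, 0.67, 0.50 |
| 5% | 0.923, 0.967, 0.979 | 2.50, 1.67, 1.25 |

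At the assumed 2%, a term unrelated to withdrawal therefore appears in the table more often than not. The last column also shows that differences for single terms would be too sparse to carry much weight, which is why an overall row is needed.

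**The case against.** The strongest reply is that a comparison for the same window may already exist. The post-treatment TEAE report carries no arm restriction, and an event that first occurs after Visit 7 should appear in it. The general AE analysis is deferred to the CPMP SAP Version 5, and withdrawal potential to a sponsor guidance. Neither is available here, and either could call for both arms. This stands as a limit on the point: it cannot be said that withdrawal will be assessed without any control. It does not rescue the table, because the OA05 sentence names one arm and no visible text gives placebo the PTEAE severity reference. If both arms are intended, the sentence should still be corrected.

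It can also be said that the sentence governs only the preferred-term tables and does not exclude a listing of placebo events. That is so, but the summary is where a reader would look for the comparison.

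Two points about size also have force. First, with expected placebo counts of 0.25 to 2.5 per term, a placebo column will seldom settle the question for any one term. Second, the denominator is uncertain. Visit 801 also follows an early discontinuation visit, whereas the PTEAE definition is anchored after Visit 7, so it is unclear whether early discontinuers count. If all 125 randomised were counted, the omitted placebo group would be 125 × 1/2 = 62.5 at 1:1 down to 125 × 1/4 = 31.25 at 3:1. That changes the illustration and leaves the argument as it was.

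Finally, withdrawal can occur only in people who were exposed. That is true, but attributing an event to withdrawal still requires the background rate.

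**Conclusion.** The point holds for this table. As written, the SAP produces a single-arm PTEAE summary that cannot separate background events from a withdrawal effect, although withdrawal assessment is one of the reasons given for reporting PTEAEs. The absence of a placebo column follows directly from the text and needs no assumption. The count of 50 to 25 omitted placebo completers rests on the assumed 1:1 to 3:1 allocation. The 64% to 78% chance that an unrelated term appears (40% to 98% over rates of 1% to 5%) also rests on assumed event rates and is illustrative only.

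The consequence is modest. The table is descriptive, no data are lost, the efficacy analyses are unaffected, and the visible list of key safety events in SAP 7.18 has no PTEAE or withdrawal item. Other outputs for the same two weeks may show both arms.

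**What to change.** Amend the last sentence of SAP 7.12.2 so that PTEAEs are summarised by preferred term, and by preferred term within system organ class, for each treatment group including placebo. Add an overall row giving the number and percentage of participants with at least one PTEAE in each group. Between-group differences for single terms can be left optional, because the counts will be sparse.

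The cost is one sentence, one column and one row in a table already planned. No visit, sample or procedure is added, since the post-treatment safety visit already applies to both arms.

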7.12.3. Deaths, Other Serious Adverse Events, and Other Notable Adverse Events

TEAEs by PT will be reported.

The general summary of AEs is described in the CPMP SAP Version 5. Other AEs include

- Abuse liability and withdrawal potential following the most recent Lilly Guidance for Assessment of Abuse Potential during Clinical Development.
- Seizures FMQ both narrow and broad terms will be analyzed.

7.12.4. Neurological Exam

In this ISA, neurological exam results will be reported for the entire 10-week study period. Study OA05 will consider the following analyses for the Neurological Exam, which evaluates 6 items and will be summarized by normal/abnormal percentage by item. In addition, we will summarize shift tables for each item in the Neurological Exam.

7.12.5. Clinical Laboratory Evaluation

The general analysis of laboratory parameters is described in the CPMP SAP Version 5.

In this ISA, laboratory results will be reported for the entire 10-week study period. Study OA05 will also consider the following analyses of lab analytes used to assess renal function. The planned summaries for these analytes are the same as those that have been described in the Study

CPMP SAP Version 5; however, the reporting of these analytes will be separate from the general analysis of laboratory parameters.

- Renal data analyses:
 - Serum creatinine (change from baseline in mg/dL)
 - eGFR; Chronic Kidney Disease Epidemiology Collaboration (algorithm using serum creatinine) Algorithm: Provided by central laboratory
 - For eGFR calculation, we will summarize shift tables of eGFR changes for baseline versus postbaseline by minimum, maximum, and last observed eGFR result:
 - Category 1: Normal or increase in GFR (≥ 90 mL/min/1.73m²)
 - Category 2: Mild reduction in GFR (60 to 89 mL/min/1.73m²)
 - Category 3a: Moderate (a) reduction in GFR (45 to 59 mL/min/1.73m²)
 - Category 3b: Moderate (b) reduction in GFR (30 to 44 mL/min/1.73m²)
 - Category 4: Severe reduction in GFR (15 to 29 mL/min/1.73m²)
 - Category 5: Kidney failure (GFR <15 mL/min/1.73m² or dialysis).

Abnormal eGFR is specified below and will be summarized in the laboratory summary tables.

- Abnormal low: <90 mL/min/1.73m²
- Abnormal high: As specified by central laboratory.

7.12.6. Vital Signs and Other Physical Findings

The analysis of vital sign parameters is described in the CPMP SAP Version 5.

Vital signs will be reported separately for the 8-week treatment period and the entire 10-week study period.

7.12.7. Electrocardiograms

The analysis of ECG parameters is described in the CPMP SAP Version 5. ECG will be reported separately for the 8-week treatment period and the entire 10-week study period.

7.12.8. Suicidal Ideation or Behavior

Reporting of suicidal ideation/behavior through the Columbia Suicide-Severity Rating Scale has been described in the CPMP SAP Version 5. Suicidal ideation/behavior will be reported separately for the 8-week treatment period and the entire 10-week study period.

